## Project Details

### I. Project Introduction

**I.1** **Project to be reviewed by:**  
IRB-01

**I.2** **Project Title:**  
Effectiveness of External Vibration for Pain Relief During Peripheral Intravenous Cannulation in Adult Patients

**I.3** **Short Title (optional):**

**I.4** **Provide a short summary of the purpose and procedures of the study proposed in this IRB application.**

- **DO NOT include information on studies not proposed in this application.**
- **Use LAY terminology only. This must be easily understandable by IRB community members and nonscientists.**
- **DO NOT cut and paste technical abstracts from funding applications that may not be understood by a general audience.**

A large number of dentoalveolar (tooth extraction) procedures performed by Oral and Maxillofacial Surgeons utilize intravenous sedation. Procedures commonly performed may include surgical removal of teeth, bone grafting, surgical placement of dental implants, and removal of cysts or tumors from the jaws, among others. Obtaining peripheral intravenous (IV) cannulation often proves to be a very stressful and anxious event for the patient. The anxiety and stress from the venipuncture alone affects not only the psychological stability of the patient, but also the patient's physiology. The Buzzy vibration external stimulation device has shown to be an effective tool in pediatric venipuncture procedures. The aim of this study is to investigate the effects of the Buzzy stimulation device in pain and anxiety reduction during peripheral intravenous cannulation in an adult population.

Enrollees in this study will be patients who will undergo dental surgery with intravenous sedation. The patients who are enrolled will receive an IV either with or without the Buzzy. The Buzzy is a small vibration device which will be placed next to the IV placement site.

**I.5** **Specify your research question(s), study aims or hypotheses (do not indicate "see protocol")**

- To investigate the efficacy of the Buzzy stimulation device in pain and anxiety reduction during peripheral intravenous cannulation in an adult population.
- Determine any benefit of the Buzzy system between men and women.
- Determine any benefit of the Buzzy system between different age ranges in adults.
- Is there a site benefit with the Buzzy system?

**I.6** **Background and significance and/or Preliminary studies related to this project. (do not indicate "see protocol")**

The Buzzy is a reusable device that applies vibration to the skin surface to override the body's gate control pain pathway. It has been used effectively to reduce the discomfort of intravenous cannulation (IV placement) in pediatric patients. Also, it has been utilized to reduce the discomfort of injections in pediatric and adult patients. We are performing this study to evaluate the effectiveness of the Buzzy in reducing the discomfort associated with intravenous cannulation (IV placement) in adults.

**II.3**      ***The Principal Investigator of this study is:***  
 Faculty

**II.6**      ***Identify the key personnel. The system will automatically designate the PI and all faculty members on the project as "key personnel." For information about other team members who should be designated as "key personnel" please click on the help information.***

**III. Funding/Other Support**

**III.1**      ***Funding Sources***

**Type**      **Source**      **Grant Title**      **Name of PI on Grant**

Departmental

\* new source name

**III.3**      ***Does any member of the research team have a financial conflict of interest related to this project according to the [Conflict of Interest in Research](#) policy? If yes, please indicate which members below.***

Name	Has Conflict of Interest
[name]	No
[name]	No
[name]	No
[name]	No

**IV. Project Type**

**IV.1**      ***Do you want the IRB to give this project***  
 Regular (expedited or full board) review

**IV.2**      ***Enter the date you will be ready to begin screening subjects/collecting data for this project.***  
 Upon IRB approval

**IV.3** *Are you requesting a waiver of informed consent/authorization (subjects will not be given any oral or written information about the study)?*  
 No

## V. Other Committee Review

**V.1** *Does this project involve any substance ingested, injected, or applied to the body?*  
 • *Do not answer yes, if the involvement includes a device, wire, or instrument*  
 No

**V.2** *Are any contrast agents used for any purpose in this study?*  
 No

**V.9** *Will any subject be asked to undergo a diagnostic radiation procedure (including radiographic, nuclear medicine, DEXA)?*  
 No

**V.14** *Will any subject be asked to undergo a radiation therapy procedure (including external beam therapy, brachytherapy, or nuclear medicine therapy)?*  
 No

**V.20** *Does this project involve the deliberate transfer of recombinant or synthetic nucleic acid molecules, or DNA or RNA derived from recombinant or synthetic nucleic acid molecules, into one or more human research participant?*  
 No

**V.21** *Will any portion of this project be conducted in the CRU, or does it use any CRU resources?*  
 No

**V.22** *Will this project use any resource/patients of the HCCC?*  
 No

**V.25.a** *Will the study involve any of the following activity at UI Health Care, even if subjects or their insurance will not be billed for the item or service, and regardless of the study funding source (including studies with departmental or no funding)?*

- Procedures, tests, examinations, hospitalizations, use of Pathology services, use of clinic facilities or clinical equipment, or any patient care services, including services conducted in the Clinical Research Unit; or*
- Physician services or services provided by non-physicians who are credentialed to bill (ARNPs, Physician Assistants, etc.)*

 No

**V.26** *The study involves nursing, nursing resources or evaluates nursing practices.*  
 No

## VI. Subjects

**VI.1** *How many adult subjects do you expect to consent or enroll for this project?*  
 100

**VI.2** *What is the age of the youngest adult subject?*  
 18.0

**VI.3** *What is the age of the oldest adult subject?*  
 40.0

**VI.4** *What is the percentage of adult male subjects?*  
 50

**VI.5** *What is the percentage of adult female subjects?*  
 50

**VI.6** *How many minor subjects do you expect to consent or enroll for this project?*  
 0

**VI.13** **Describe EACH of your subject populations**

- **Include description of any control group(s)**
- **Specify the Inclusion/Exclusion criteria for EACH group**
- **Studies under IRB-03 enrolling non veterans as part of the subject population must present a compelling argument to the IRB for the inclusion of non-Veterans (e.g., insufficient number of Veterans; survey of VA employees; study of active duty military; study involving Veterans' family members), and the research is relevant to the care of Veterans or active duty military personnel.**

The study will be preformed on patients undergoing intravenous sedation for dental surgery.

This study is intended to be equally inclusive of male and female patients. An inclusion criterion is to be between ages 18 and 40. There are no medical conditions which would preclude participation in the study.

The control group (50% of total subjects) will have an IV started in the standard fashion.

The experimental group (50% of total subjects) will have an IV started in the standard fashion with use of the Buzzy.

**VI.14** **Provide an estimate of the total number of subjects that would be eligible for inclusion in each of your study populations (include your control population if applicable)**

The majority of the patient population treated by Oral and Maxillofacial Surgery is adults. All adults aged 18 to 40 who are receiving intravenous sedation for their dental surgery will be eligible for inclusion in the study. There are approximately forty patients per week at the college of dentistry who meet these criteria.

**VI.15** **Describe how you will have access to each of your study populations in sufficient number to meet your recruitment goals.**

The Oral and Maxillofacial Surgery department does approximately 2000 IV sedations at the UI College of Dentistry and Dental Clinics each year.

**VI.16** **Do you plan to recruit/enroll non-English speaking people?**

No

**VI.18** **Do you propose to enroll any of the following in this study as subjects?**

- **Employee of the PI or employee of a research team member**
- **Individual supervised by PI or supervised by member of research team**
- **Individual subordinate to the PI or subordinate to any member of the research team**
- **Student or trainee under the direction of the PI or under the direction of a member of the research team**

No

**VI.20** **Will subjects provide any information about their relatives?**

No

**VI.23** **Will anyone (other than the subject) provide you with information about the subject (e.g. proxy interviews)?**

No

**VI.26** **Is this project about pregnant women?**

No

**VI.27** **Will this project involve fetuses?**

No

**VI.28** **Does this project involve adult subjects who may be incompetent or have limited decision-making capacity on initial enrollment into the study?**

No

**VI.32** **Does this project involve subjects whose capacity to consent may change over the course of the study?**

No

**VI.37** **Does this project involve prisoners as subjects?**

No

**VII.A. Project Description (A)**

**VII.A.1** **Where will project procedures take place (check all that apply)?**

- Other UI campus site - College of Dentistry Oral and Maxillofacial Surgery Clinic

**VII.A.2** **Is this project also being conducted by other researchers at their own sites (e.g. a multi-site collaborative project)?**

No

## VII.B. Project Description (B)

**VII.B.1** **Does this project involve any of the following (Check all that apply):**

- Registry** – The collection and maintenance of data (not including biologic samples) in which: (1) the individuals in the registry have a common or related condition(s), and/or (2) the individuals in the registry are interested in being contacted for future studies by investigators other than those listed in Section II of this project. ([UI Guide](#))
- Repository** – The collection, storage, and distribution of human biologic samples and/or data materials for research purposes. Repository activities involve three components: (i) the collection of data and/or specimens such as blood, tissue, saliva, etc.; (ii) the storage of data or specimens, and data management function; and (iii) the sharing of data/specimens with recipient investigators other than the original investigators. (paraphrased from [OHRP](#))
- Expanded Access** – A process regulated by the Food and Drug Administration (FDA) that allows manufacturers to provide investigational new drugs to patients with serious diseases or conditions who cannot participate in a clinical trial. Examples of expanded access include non-protocol access to experimental treatments, including protocol exception, single-patient IND, treatment IND, compassionate use, emergency use, continued access to investigational drug, and parallel track ([ClinicalTrials.gov](#) & [FDA](#)).
- Clinical (or Treatment) trial** – A prospective biomedical or behavioral research study of new treatments, new drug or combinations of drugs, new devices, or new approaches to surgery or radiation therapy. (NIH and [ClinicalTrials.gov](#) & [FDA](#))
- Physiology intervention/study** – A pharmacologic or measurement study aimed at understanding basic mechanisms of disease and/or of normal human physiology, often without any therapeutic intent (though a clinical trial could include such components, often labeled as "translational" or "basic science" aims.) Measurements in such studies could include, but are not limited to, a blood draw, EKG, EEG, MRI, auditory or sensory testing, checking vital signs, DEXA scans, eye tracking, specimen collection, exercise, fasting, special diets, etc.
- Behavioral intervention/study** – May be used to refer to studies of individual or group behavior. This option does not include drugs, biologics, or devices but could include psychotherapy, lifestyle counseling, behavior modification, etc.
- Diagnostic trial** – Protocol designed to evaluate one or more interventions aimed at identifying a disease or health condition ([ClinicalTrials.gov](#) & [FDA](#))
- Non-clinical** – any college/department that would regularly submit to [IRB-02](#)
- Other – Describe:**  
Survey involving application of external vibration device while placing peripheral IV.

**VII.B.1.b** **Provide the [NCT](#) (National ClinicalTrials.gov Identifier) number**  
NCT03619135

**VII.B.2** **Does this project involve a [drug washout](#) (asking subject to stop taking any drugs s/he is currently taking)?**  
No

**VII.B.6** **Will any subjects receive a [placebo](#) in this study when, if they were not participating, they could be receiving an FDA-approved treatment for their condition?**  
No

**VII.B.11** **Is there a separate, written protocol that will be submitted in addition to this IRB New Project form? (Note: a grant application is not considered to be a protocol)**  
No

**VII.B.18** **Does this project involve testing the safety and/or efficacy of a medical device?**  
Yes

**VII.B.19** **Describe in detail procedures in place for maintaining device shipment and receipt records:**  
The Buzzy units are reusable medical devices and as such, all device records will be maintained per standard departmental protocol by nursing at the College of Dentistry Department of Oral and Maxillofacial Surgery under supervision of the PI.

**VII.B.20** **Who will be responsible for maintaining these shipment and receipt records?**  
N/A

**VII.B.21** **Describe in detail procedures in place for tracking use and disposition of devices described in this study:**  
All patients included in the study will have their record number noted on the study questionnaire should this be required for later use. The device is reusable and not implanted.

**VII.B.22** **Who will be responsible for maintaining these use and disposition tracking records?**  
The study team/PI.

**VII.B.23** **Describe in detail procedures in place to limit access to authorized study personnel for the storage, control, and dispensing of the investigational devices. (For example, investigational devices are kept in a locked area away from approved devices or have a keyed interlock, and only study personnel authorized to dispense the device have the keys)**  
The device will be maintained in the dispensary at the College of Dentistry Department of Oral and Maxillofacial Surgery. The device is not dispensed and is available to the public for purchase and is not of concern for abuse.

**VII.B.24** **Is the device FDA-approved for the way it will be used in this study?**  
Yes

### VII.C. Project Description (C)

**VII.C.1** **Does this project involve any research on genes or genetic testing/research?**  
No

### VII.D. Project Description (D)

**VII.D.1** **Check all materials/methods that will be used in recruiting subjects (you will need to attach copies of all materials at the end of the application):**

- Brochures -
- Use of any information available to the researchers or their colleagues because this person is a patient OR use of any information considered to be Protected Health Information (PHI) OR review of patient/clinic records - This study will use subjects already planned for surgical removal of third molars with the use of intravenous sedation. The study will be explained (both verbally and with the written form) to the patients at the beginning of their surgical appointment. The patient will be given the opportunity to discuss participation with their escort (typically a family member or friend and always an adult) as needed.

**VII.D.2** **List the individual data elements you will need to access/use from the patient or clinic records to identify potential subjects for recruitment**  
Age and planned sedation

**VII.D.3** **Describe why you could not practically recruit subjects without access to and use of the information described above**  
These two pieces (age and planned sedation) of information are our two inclusion criteria

**VII.D.4** **Describe why you could not practically obtain authorization from potential subjects to review their patient or clinic records for recruitment purposes.**  
Age and whether the procedure are planned are two inclusion criteria which must be known in order to ask the patient to participate in the study

**VII.D.5** **Describe plans to protect the identifiers from improper use or disclosure**  
There is no written information kept on potential subjects.

**VII.D.6** **Describe plans to destroy identifiers at the earliest opportunity consistent with conduct of the research**  
There is nothing to destroy since no written information has been stored.

**VII.D.7** **Does the research team agree that the requested information will not be reused or disclosed to any other person or entity, except as required by law, for authorized oversight of the study, or for other research for which the use or disclosure of the requested information would be permitted by the HIPAA Privacy Rule**  
Yes

**VII.D.8** **Will a member of the research team discuss the study with the subject in person prior to the subject**

**agreeing to participate?**  
Yes

**VII.D.9      Describe the physical location where the consent process will take place:**  
The patient (subject) will be recruited and agree to (or deny) participate in this study in a surgical treatment room in the Oral and Maxillofacial Surgery Clinic at the University of Iowa College of Dentistry.

**VII.D.10     Will a member of the research team discuss the study with the subject by phone prior to the subject agreeing to participate?**  
No

**VII.D.12     Who will be involved in the consent process (including review of consent document, answering subjects' questions)?**

Name	Consent Process Involvement
[name]	Yes
[name]	Yes
[name]	Yes
[name]	Yes

**VII.D.15     Check all materials that will be used to obtain/document informed consent:**

- Consent Document

**VII.D.16     Are you requesting a waiver of documentation of consent (either no subject signature or no written document)?**  
No

**VII.D.19     Before the subject gives consent to participate are there any screening questions that you need to directly ask the potential subject to determine eligibility for the study?**  
No

**VII.D.25     After the subject agrees to participate (signs consent), are there any screening procedures, tests, or studies that need to be done to determine if the subject is eligible to continue participating?**  
No

**VII.D.27     Discuss how much time a potential subject will have to agree to consider participation and whether or not they will be able to discuss the study with family/friends before deciding on participation.**  
We will use subjects planned for third molar removal with IV sedation (previously informed of the IV process). The study will be explained (verbal and written) to the patient at the start of their visit. The patient will have the opportunity to discuss participation with their escort (always an adult family member/friend) as needed. They will need to decide within a few minutes if they wish to participate.

**VII.D.28     How long after the subject agrees to participate do study procedures begin?**  
After the patient agrees to participate.

**VII.D.29     Provide a description of the enrollment and consent process for adult subjects**

- **Describe each study population separately including control population**
- **Include when recruitment and consent materials are used**
- **Use 3rd person active voice "The Principal Investigator will identify subjects. For example, the principal investigator will identify potential subjects, the study coordinator will discuss the study with subjects over the telephone and schedule the first study visit, etc..."**
- **Describe the steps that will be taken by the research team to minimize the possibility of coercion or undue influence during the consent process**

The potential subjects will be encountered in the oral surgery clinic. They will be seated in the procedure room. If the patient meets study criteria they will be asked if they would like to participate in the study. They will be able to review the recruitment brochure at that time in the clinic. The potential subject will then be approached a member of the research team who can further describe the study. A member of the research team will go over the consent document with the subject. It will be explained that there are no potential risks or complications involved with the use of the Buzzy. To minimize coercion we will inform that patient that there is no obligation to participate in the study and that participation is voluntary.

**VII.D.37     Does the study include any form of deception (e.g., providing participants with false information, misleading information, or withholding information about certain study procedures)?**

**Examples:**

- **Procedure includes a cover story that provides a plausible but inaccurate account of the purposes of**

*the research.*

- **Participants will be provided with false information regarding the particular behaviors of interest in the research.**
- **Procedures include a confederate pretending to be another participant in the study.**
- **Participants will be told that the research includes completion of a particular task, when in fact, that task will not be administered.**
- **Study is designed to introduce a new procedure (or task) that participants are not initially told about.**
- **If yes, a waiver of informed consent must be requested under question IV.3.**

No

## VII.E. Project Description (E)

**VII.E.1**      **Will subjects be randomized?**  
Yes

**VII.E.1.a**      **Will any subjects be blinded to which study arm they have been assigned?**  
No

**VII.E.2**      **Describe randomization scheme/assignment including ratio such as 1:1, 2:1 etc.**  
The study will be made of two randomized groups with a 1:1 ratio. Those who use the Buzzy system (experimental group) and normal, routine IV start without Buzzy (control).

An equal number of forms noting Buzzy (experimental) and Standard (control) will be printed and placed in security envelopes. These will be randomly mixed and when an eligible and participating subject is identified, the top most envelope will be chosen and opened to assign the group.

**VII.E.3**      **Will any questionnaires, surveys, or written assessments be used to obtain data directly from subjects in this study?**  
Yes

**VII.E.4**      **List all questionnaires, surveys, written assessments and ATTACH each one to the application. (NOTE: You are NOT prohibited from attaching copyrighted materials to this application)**  
A single questionnaire with before and after placement of intravenous catheter

**VII.E.5**      **Does this project involve creating any audiotapes, videotapes, or photographs?**  
No

**VII.E.6**      **Provide a detailed description in sequential order of the study procedures following the consent process - DO NOT cut and paste from the Consent Document.**

**Describe study populations separately if they will be participating in different procedures - include CONTROL population if applicable.**

### DESCRIBE:

- **What subjects will be asked to do/what happens in the study (in sequential order)**
- **The time period over which procedures will occur**
- **The time commitment for the subject for individual visits/procedures**
- **Long-term followup and how it occurs**

The participants will be randomized into two groups, those who use the Buzzy system (experimental), and routine IV start (control). Prior to knowing their group, all patients will answer the "Before Intravenous Catheterization" portion of the form in order to eliminate bias. After this portion is complete, their group (experimental vs control) will be determined from opening a blinded envelope.

A tourniquet will be placed, followed by the Buzzy stimulation device (if in the experimental group). An alcohol swab will be used and then a 22 gauge IV catheter will be inserted, connected to fluids, and secured with tape. The antecubital fossa or the dorsal hand/wrist will be the only sites used in the study. All participants will fill out the post-insertion questions on the form and those patients that used the Buzzy system will then fill out the several specific questions related to the experimental group. This will conclude the patient's involvement in the study. The patient will then continue with treatment as planned. We will plan to exclude cases where the IV is not obtained on the first attempt, if a smaller or larger gauge IV catheter is required, or if an insertion site not listed above is required. The case will be excluded if adjunctive steps are taken to obtain IV access (i.e. Oral sedation, nitrous oxide, heat packs).

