## XI. Data Analysis

**XI.1** **Describe the analysis methods you will use, including, if applicable, the variables you will analyze**  
Simple descriptive statistics would be used to summarize the data. Normality of data will be assessed by Kolmogirov Smirnov test. Continuous outcomes would be assessed by t-tests, ANOVA, and multivariable linear regression models. Categorical variables would be assessed by Chi-square tests and multivariable logistic regression models. All tests will be two sided and a p-value of <0.05 would be set for statistical significance.

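### Patients answer Before questions ahead of allocation, but XI.1 gives those answers no role in the between-arm comparison, so available precision may go unused

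*Combined protocol and SAP*

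**What the plan says.** The first aim in I.5 concerns "pain and anxiety reduction during peripheral intravenous cannulation in an adult population". Section VII.E.4 describes the instrument as "A single questionnaire with before and after placement of intravenous catheter". Under VII.E.6 all patients answer the Before "portion of the form in order to eliminate bias", and the order is explicit: "After this portion is complete, their group (experimental vs control) will be determined from opening a blinded envelope". Afterwards, "All participants will fill out the post-insertion questions on the form", and the Buzzy arm answers some further items.

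On analysis, XI.1 says "Continuous outcomes would be assessed by t-tests, ANOVA, and multivariable linear regression models", and sends categorical variables to chi-square tests and logistic regression. It names no anxiety outcome, no covariate and no use for the Before answers. XI.2 sizes the trial on a single Wong-Baker FACES score, with no baseline term and no anxiety assumption. VII.B.11 states that there is no separate protocol, so XI.1 is the only place where the choice could be fixed.

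**The concern.** The data collection is sound. A measurement completed before the arm is known cannot be affected by the allocation, which makes it a legitimate covariate. The gap is in XI.1, which does not use it.

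The wording fits at least three between-arm analyses: the after score alone, the after-minus-before change, and the after score adjusted for the Before answer. All three estimate the arm effect without bias, but their precision differs, and the choice could be made after the data are seen. If the Before answer predicts the after answer, the first gives up precision. The second gives up more than the first when the correlation is below 0.5. At stake are the width of the confidence interval for anxiety, and for pain too if the Before rating predicts it.

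**Working it through.** **Inputs from the documents (XI.1, XI.2).** Difference 2, SD 3.10, two-sided alpha 0.05, power 80%, 38 per arm (76 in total), up to 100 enrolled.

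**Inputs assumed.** Before/after correlation ρ = 0.3, 0.5 or 0.7, and equal SDs before and after. The documents give neither ρ nor an anxiety SD, so the FACES pain figures stand in for scale only.

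**1. The plan's own figure.** n per arm = 2 × SD² × (1.960 + 0.842)² / difference² = 2 × 9.61 × 7.849 / 4 = 37.7, rounded up to 38. This matches XI.2. It is a two-sided comparison of one score with no baseline term. The noncentral t distribution gives 79.3% power at 38 per arm, and the normal approximation 80.3%. The noncentral-t values are used below.

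**2. Residual SD under each analysis.**
- After score alone: SD
- Change score: SD × √(2(1 − ρ))
- After score adjusted for Before (ANCOVA): SD × √(1 − ρ²)

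**3. Variance relative to the after score alone.**
- Change, 2(1 − ρ): 1.4, 1.0, 0.6 at ρ = 0.3, 0.5, 0.7
- ANCOVA, 1 − ρ²: 0.91, 0.75, 0.51, a reduction of 9%, 25% or 51%

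**4. Power at 38 per arm, difference 2.**

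| ρ (assumed) | After only | Change | ANCOVA (residual SD) |
|---|---|---|---|
| 0.3 | 79.3% | 65.0% | 82.9% (2.96) |
| 0.5 | 79.3% | 79.3% | 89.3% (2.68) |
| 0.7 | 79.3% | 94.8% | 97.3% (2.21) |

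The change column also needs the before and after items to be on the same scale. ANCOVA does not. Its price is one degree of freedom, which does not alter these figures at the precision shown.

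**5. At the enrolment cap.** With 50 per arm and no exclusions, the same formulas give 89% for the after score alone and 92%, 96% and 99% for ANCOVA. The gain shrinks as power approaches its ceiling, but the proportional cut in variance is unchanged.

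**6. Why a note on within-arm tests is worth adding.** In a simulation (20,000 runs, 38 per arm, SD 3.10, no device effect, both arms assumed to fall by 1 point), separate before/after tests in each arm disagreed on significance in 42% to 50% of trials for ρ from 0.3 to 0.7. A direct between-arm test is wrong in 5%. The plan does not propose such tests, so this supports a safeguard and is not an estimate of the plan's error rate.

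**The case against.** The strongest objection is that the Before section has not been seen. It is an attachment outside the reviewed text. It might hold demographics, past experience of IVs, expected pain or a yes/no fear item. No section names an anxiety scale. This stands: that the section holds an anxiety rating is inferred from the anxiety aim and from the care taken to collect the answers before allocation.

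Second, the power figures borrow pain inputs for an anxiety question. This also stands. They show how adjustment scales with ρ and are not the trial's power for anxiety.

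Third, XI.1 already lists multivariable linear regression. It does, and that model could carry the covariate. But no baseline term is named, and nothing says whether the regression or the t-test governs the conclusion.

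A reader might also infer three stronger points, which the documents do not support:
- **That efficacy will be judged by before/after change within an arm.** No section proposes this. VI.13, VII.E.2 and VII.E.6 describe a randomised control group, XI.2 is a two-group calculation, and the reduction in I.5 reads naturally as less pain and anxiety than without the device.
- **That an after-only or change-score comparison is invalid.** Between randomised arms either is unbiased. A change score is noisier than the after score only when ρ is below 0.5, and is better above it.
- **That the sample size is wrong.** It reproduces.

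**Conclusion.** The concern holds as a matter of precision and pre-specification, not of bias. XI.1 should say how the Before answers enter the between-arm model, and at present it does not. If the section contains an anxiety rating that correlates 0.3 to 0.7 with the later one, adjustment removes 9% to 51% of the residual variance. On the borrowed pain inputs that moves power from 79% to between 83% and 97%. For the FACES pain score the gain depends on whether the Before rating predicts pain, about which the documents say nothing. The conclusion rests on the assumed content of the form and the assumed correlations. If the Before section holds no anxiety item, the anxiety adjustment cannot be done as described, and XI.1 should instead name whichever Before answer is to be used, if any.

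**What to change.** In XI.1:

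- Name the anxiety item on the questionnaire. Make the main anxiety analysis a between-arm comparison of the post-insertion anxiety score by linear regression on arm plus the patient's own Before anxiety rating (ANCOVA), reporting the adjusted difference with a 95% confidence interval.
- If the item is categorical, use logistic regression with arm and the same covariate.
- Pre-specify the Before rating as a covariate in the model for the FACES pain score.
- State that any before/after comparison within an arm is descriptive only. This is a safeguard, since the plan proposes none.

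The cost is a few sentences, plus checking the form to confirm what the Before section asks. If it does hold an anxiety rating, no extra data, visits or patients are needed, and the sample size can stay as it is.
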